5.1.1 Immune Phenotyping

Exploratory immunologic studies will be conducted to evaluate the study drug's effect on the immune response before and after treatment, to gain insight into potential biomarkers, and help improve the administered therapy. Blood will be collected as per the **Study Calendar**. The following immune assays may be performed at the Laboratory of Tumor Immunology and Biology (LTIB) at the NCI's Center for Cancer Research (CCR) in select participants where adequate samples are available:

1. PBMCs may be analyzed for changes in standard immune cell types (CD4 and CD8 T cells, natural killer [NK] cells, regulatory T cells [Tregs], myeloid-derived suppressor cells

[MDSCs], and dendritic cells) as well as 123 immune cell subsets, using multi-color flow cytometry.

2. PBMCs from selected subjects may be analyzed for function of specific immune cell subsets, including CD4 and CD8 T cells, NK cells, Tregs, and MDSCs using flow-based assays.
3. PBMCs may be analyzed for tumor antigen-specific immune responses using an intracellular cytokine staining assay. PBMCs will be stimulated in vitro with overlapping 15-mer peptide pools encoding the tumor-associated antigens HPV 16 E6 and E7 and HPV18 E6 and E7; control peptide pools will involve the use of human leukocyte antigen peptide as a negative control and CEFT peptide mix as a positive control. CEFT is a mixture of peptides of CMV, Epstein-Barr virus, influenza, and tetanus toxin. Post-stimulation analyses of CD4 and CD8 T cells will involve the production of IFN- γ , IL-2, TNF, and the degranulation marker CD107a. If sufficient PBMCs are available, assays may also be performed for the development of T cells to other tumor-associated antigens.

5.1.2 Soluble Factors

Samples for soluble factor analysis will be collected as per the [Study Calendar](#).

Sera may be analyzed pre- and post-therapy for the following soluble factors: sCD27, sCD40 ligand using commercial ELISA kits.

Sera may be analyzed for changes in cytokines (IFN- γ , IL-10, IL-12, IL-2, IL-4, etc.), chemokines, antibodies, tumor-associated antigens, and/or other markers using ELISA or multiplexed assays (e.g., Mesoscale, Luminex, cytokine bead array).

5.1.3 AVA

Anti-vector antibodies (AVA) are one mechanism of neutralization and inefficacy of viral vectors. Longitudinal detection and titer measurement of AVA to the vaccine adenoviral vector will assist in characterizing cases of loss of efficacy.

5.1.4 M7824 Pharmacokinetics

PK measurements of M7824 will be taken in Arm 1B only to collect data which will provide insight into population PKs of M7824 in participants receiving these novel combinations.

The schedule is in the [Study Calendar](#). Serum M7824 PK measurements will be done at EMD Serono.

5.1.5 ADA

Anti-Drug Antibody (ADA) development is an accepted mechanism of loss of efficacy of administered human monoclonal antibodies. Measuring titers will ensure that lack of efficacy of M7824 is not due to ADA development.

The schedule is in the Study Calendar – samples will be collected in Arm 1B only. The investigation will be done by EMD Serono using ELISA.

5.1.6 Tumor Tissue Analyses for Immune Markers

Analyses may be performed in pre-treatment vs. post-treatment (at Week 4-5 for phase II participants) tumor tissue. Where available, archival tumor samples may be requested for pre-treatment analysis (preferably tissue samples from the last 6 months). For participants with lesions amenable to biopsy, two biopsies may be performed at baseline and at Week 4-5 (phase II participants) or Week 9 (phase I participants). Tumor samples will be sent to the Laboratory of Pathology for disease evaluation; remaining samples will be used for research. Tissue samples for research may also be stored in CSP as described in Section [5.2.1](#).

Where available, study of immune infiltration as well as PD-L1 status within the tumor microenvironment pre vs. post treatment by IHC and/or multiplex immunofluorescence may be performed by the GMB TIME Laboratory.

5.1.7 Single-cell proteomic analysis

Where available, tumor tissue single-cell proteomic analysis of immune and signaling pathways may be performed with the Isoplexis Single Cell Functional proteomic platform by Precigen.

5.1.8 Immune transcriptomic analysis

Where available, tumor tissue immune transcriptomic analysis may be performed with the Nanostring platform by Precigen.

5.1.9 Additional Biomarker Studies

De-identified, coded blood (PBMC, plasma, and/or serum) or tissue samples may be sent to Precigen Inc., the manufacturer of PRGN-2009, to further investigate HPV 16/18 -specific immune responses, activation status of the immune system (e.g., leukocyte subsets, exhaustion, cytokines profile), antigen cascade, anti-tumor specific immune responses induced by the exposure to PRGN-2009, and potential predictive/prognostic biomarker candidates related to the drug and/or cancer (e.g., specificity of tumor infiltrating cells), and results of these analyses will be shared with the NCI. These analyses are exploratory and dependent on the quality and availability of sufficient materials. The panel of biomarkers might be adjusted based on results from ongoing research; therefore, any remaining samples can be stored at Precigen and can be used for future exploratory research on the drug and/or disease-related aspects. Only remaining samples will be used to this purpose, no additional samples will be collected.

5.1.10 Assessment of HPV status

In participants with available tumor tissue (either archival or by optional biopsy), HPV testing will be performed using the Roche Cobas or Becton Dickinson HPV PCR based DNA assay, if no prior HPV testing of the tumor has been performed. This will be done through collaboration with [name].

5.1.11 Circulating tumor DNA

If sufficient plasma is available, select participant samples may be analyzed for circulating tumor DNA (LTIB and NCI Frederick Genomic Core Facility). Plasma DNA will be isolated with an automated purification system. The circulating tumor/HPV DNA will be quantified with a digital droplet PCR system from Bio-Rad to obtain precise quantification. This is just quantification by PCR. There is no DNA sequencing.

Abbreviated Title: Combo Immunotx in HPV OPSCC

Version Date: 09.20.2023

5.1.12 RNA and T-cell Receptor Clonality Analysis of Blood and Tumor Tissue

Where possible, RNA expression and T-cell receptor clonality analysis will be done on the peripheral blood as well as archived tumor tissue or optional biopsies to help further evaluate changes in immune response and RNA expression levels with treatment as well as to determine tumor and infiltrating lymphocyte characteristics which may be predictive of response to treatment. In addition, these analyses will also be used to gauge resistance mechanisms and additional targets for future therapy. Coded, linked samples may be analyzed for RNA expression levels using the Nanostring platform and T-cell receptor clonality using the ImmunoSeq platform (LTIB and NCI Frederick Genomic Core Facility).

NCI Fredrick Genomic Core Facility:

Leidos Biomedical Research, Inc:

[name]

[name]

[name]

Ph. [contact]

5.1.13 Salivary HPV DNA

Participants in Phase 2 Cohort 2 with p16-positive oropharyngeal cancer will have collection of saliva by mouth rinse and gargle with 15-20 mL 0.9% NaCl for 30 seconds and spitting into the collection tube (timepoints per [Study Calendar](#)). Where possible, saliva samples will be analyzed for HPV DNA detection and quantification (LTIB and NCI Frederick Genomic Core Facility). Salivary HPV DNA will be quantified with digital droplet PCR; no sequencing is involved.

5.2 SAMPLE STORAGE, TRACKING AND DISPOSITION

Samples will be ordered in CRIS and tracked through a Clinical Trial Data Management system. Should a CRIS screen not be available, the CRIS downtime procedures will be followed. Samples will not be sent outside the National Institutes for Health (NIH) without appropriate approvals and/or agreements, if required.

5.2.1 Sample Management and Storage at Clinical Services Program – Leidos Biomedical Research, Inc. (CSP)

Clinical Services Program - Leidos Biomedical Research, Inc.

Attn: [name]

[name]

[name]

[name]

On days samples are drawn, [name] at CSP (part of NCI Frederick Central Repositories) should be notified (phone: [name]; fax: [name]). She will arrange same-day courier delivery of the specimens.

All data associated with the participant samples is protected by using a secure database. All Clinical Support Laboratory Staff receive training in maintaining records' confidentiality. All samples drawn at the NIH Clinical Center will be transported to the Clinical Support Laboratory at the Frederick National Laboratory for Cancer Research by couriers.

Abbreviated Title: Combo Immunotx in HPV OPSCC

Version Date: 09.20.2023

Samples will be tracked and managed by Central Repository database, where there is link to personal identifiable information. All samples will be stored in either a -80°C freezer or vapor phase liquid nitrogen. These freezers are located at NCI Frederick Central Repository in Frederick, Maryland.

NCI Frederick Central Repositories (managed under a subcontract) store, among other things, biological specimens in support of NIH clinical studies. All specimens are stored in secure, limited-access facilities with sufficient security, backup, and emergency support capability and monitoring to ensure long-term integrity of the specimens for research.

Specimens are stored in accordance with applicable HHS and FDA Protection of Human Subjects Regulations in accordance with the subcontractor's Federal-wide Assurance. The subcontractor's role limited to clinical research databases and repositories containing participant specimens. The subcontractor does not conduct or have any vested interest in research on human subjects but does provide services and support the efforts of its customers, many of which are involved in research on human subjects.

It is the intent and purpose of the subcontractor to accept only coded, linked samples and sample information. To the limit of our ability, every effort will be made to ensure that protected information is not sent electronically or by hard copy or on vial labels.

Sample data is stored in the Biospecimen Inventory System II (BSI). This inventory tracking system is used to manage the storage and retrieval of specimens as well as to maintain specimen data. BSI is designed for controlled, concurrent access. It provides a real-time, multi-user environment for tracking millions of specimens. The system controls how and in what order database updates and searches are performed. This control prevents deadlocks and race conditions. For security, BSI has user password access, 3 types of user access levels, and 36 user permissions (levels of access) that can be set to control access to the system functions. BSI provides audit tracking for processes that are done to specimens including shipping, returning to inventory, aliquoting, thawing, additives, and other processes. BSI tracks the ancestry of specimens as they are aliquoted, as well as discrepancies and discrepancy resolution for specimens received by the repository. If a specimen goes out of the inventory, the system maintains data associated with the withdrawal request. Vials are labeled with a unique BSI ID which is printed in both eye-readable and bar-coded format. No patient-specific information is encoded in this ID.

Investigators are granted view, input, and withdrawal authority only for their specimens. They may not view specimen data or access specimens for which they have not been authorized. Access to specimen storage is confined to repository staff. Visitors to the repositories are escorted by repository staff at all times.

5.2.2.2 Sample Data Collection

All samples sent to the Blood Processing Core (BPC) will be barcoded, with data entered and stored in the Labmatrix utilized by the BPC. This is a secure program, with access to Labmatrix limited to defined [name] lab personnel, who are issued individual user accounts. Installation of Labmatrix is limited to computers specified by [name]. These computers all have a password restricted login screen. All [name] lab personnel with access to participant information are required to complete the Human Subjects Research course.

Labmatrix creates a unique barcode ID for every sample and sample box, which cannot be traced back to participants without Labmatrix access. The data recorded for each sample includes the patient ID, name, trial name/protocol number, time drawn, cycle time point, dose, material type, as well as box and freezer location. Participant demographics associated with the clinical center patient number are provided in the system. For each sample, there are notes associated with the processing method (delay in sample processing, storage conditions on the ward, etc.).

5.2.2.3 Sample Storage

Barcoded samples are stored in barcoded boxes in a locked freezer at either -20 or -80 °C according to stability requirements. These freezers are located onsite in the BPC and offsite at NCI Frederick Central Repository Services in Frederick, MD. Visitors to the laboratory are required to be accompanied by laboratory staff at all times.

Access to stored clinical samples is restricted. Samples will be stored until requested by a researcher named on the protocol. All requests are monitored and tracked in Labmatrix. All researchers are required to sign a form stating that the samples are only to be used for research purposes associated with this trial (as per the IRB approved protocol) and that any unused samples must be returned to the BPC. It is the responsibility of the NCI Principal Investigator to ensure that the samples requested are being used in a manner consistent with IRB approval.

5.2.3 Procedures for Storage of Tissue Specimens in the Laboratory of Pathology

Tissues designated for clinical diagnostics are transported to the Laboratory of Pathology (LP) where they are examined grossly and relevant portions are fixed, embedded in paraffin and sectioned and stained for diagnostic interpretation. Unutilized excess tissues are stored for up to three months, in accordance with College of American Pathologists/Joint Commission on Accreditation of Healthcare Organizations (CAP/JCAHO) guidelines, and then discarded. Following completion of the diagnostic workup, the slides and tissue blocks are stored indefinitely in the LP's clinical archives. All specimens are catalogued and retrieved utilizing the clinical laboratory information systems, in accordance with CAP/JCAHO regulations. The use of any stored specimens for research purposes is only allowed when the appropriate IRB approval has been obtained. In some cases, this approval has been obtained via the original protocol on which the participant was enrolled.

5.2.4 Protocol Completion/Sample Destruction

All specimens obtained in the protocol are used as defined in the protocol. Any specimens that are remaining at the completion of the protocol will be stored in the conditions described above. The study will remain open so long as sample or data analysis continues. Samples from consenting

subjects will be stored until they are no longer of scientific value. If, at any time, a participant withdraws from the study and does not wish for their existing samples to be utilized, the individual must provide a written request. Following receipt of this request, the samples will be destroyed (or returned to the participant, if so requested). The PI will report any loss or unanticipated destruction of samples per Section 7.2.1. If the participants withdraws consent the participant's data will be excluded from future distributions, but data that have already been distributed for approved research use will not be able to be retrieved.

Sample barcodes are linked to participant demographics and limited clinical information. This information will only be provided to investigators listed on this protocol, via registered use of the Labmatrix. It is critical that the sample remains linked to participant information such as race, age, dates of diagnosis and death, and histological information about the tumor, in order to correlate genotype with these variables.

6 DATA COLLECTION AND EVALUATION

6.1 DATA COLLECTION

The PI will be responsible for overseeing entry of data into a 21 CFR Part 11-compliant data capture system provided by the NCI CCR and ensuring data accuracy, consistency and timeliness. The principal investigator, associate investigators/research nurses and/or a contracted data manager will assist with the data management efforts. Primary and final analyzed data will have identifiers so that research data can be attributed to an individual human subject participant.

All adverse events, including clinically significant abnormal findings on laboratory evaluations, regardless of severity, will be followed until return to baseline or stabilization of event. Document AEs from the first study treatment, study day 1, through 28 days after the subject received the last product administration. After 28 days, only adverse events which are serious and related to the study investigational agent need to be recorded. For participants enrolled on the phase II portion of the protocol adverse events which occur while participant is being treated with standard chemoradiation and which are not attributed to immunotherapy need not be captured.

An abnormal laboratory value will be recorded in the database as an AE **only** if the laboratory abnormality is characterized by any of the following:

- Results in discontinuation from the study;
- Is associated with clinical signs or symptoms;
- Requires treatment or any other therapeutic intervention;
- Is associated with death or another serious adverse event, including hospitalization;
- Is judged by the Investigator to be of significant clinical impact; and/or
- If any abnormal laboratory result is considered clinically significant, the investigator will provide details about the action taken with respect to the test drug and about the participant's outcome.

End of study procedures: Data will be stored according to HHS, FDA regulations, and NIH Intramural Records Retention Schedule as applicable.

Loss or destruction of data: Should we become aware that a major breach in our plan to protect subject confidentiality and trial data has occurred, this will be reported expeditiously per requirements in Section [7.2.1](#).

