3.3.3 Study Accrual Halting Rules

Accrual will be halted if:

- Phase 1 and Phase 2:
 - There is an occurrence of any death (other than death related to progressive disease or accidental death) that occurs within 30 days of administration of study agents (PRGN-2009 and M7824) for both Phase 1 and Phase 2.
- Phase 2 only:
 - There is a delay in initiation of definitive standard of care therapy of 4 weeks or more beyond the planned start date due to treatment-related toxicities from HPV vaccine in two participants.

- There is occurrence of treatment-related ADRs from HPV vaccine of either Grade 4 (except for laboratory values that are asymptomatic or resolve to Grade ≤ 1 or baseline within 7 days) or of Grade 3 not resolving to Grade ≤ 1 or baseline within 7 days in two participants.

The IRB and the sponsor will be notified if one of the study accrual halting rules has been reached.

The accrual halt will be lifted once the data has been reviewed and there has been a reassessment of available safety information prior to reopening the study to accrual and allowing the study to proceed.

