8 SPONSOR PROTOCOL / SAFETY REPORTING

8.1 DEFINITIONS

8.1.1 Adverse Event

Any untoward medical occurrence in a patient or clinical investigation subject administered a pharmaceutical product and which does not necessarily have a causal relationship with this treatment. An adverse event (AE) can therefore be any unfavorable and unintended sign (including an abnormal laboratory finding), symptom, or disease temporally associated with the use of a medicinal (investigational) product, whether or not related to the medicinal (investigational) product (ICH E6 (R2)).

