8.4 WAIVER OF EXPEDITED REPORTING TO CCR

As death/hospitalization due to disease progression is/are part of the study objectives, and captured as an endpoint in this study, they will not be reported in expedited manner to the sponsor. However, if there is evidence suggesting a causal relationship between the study drug and the event, report the event in an expedited manner according to Section [8.3](#)

As M7824 is known to result in immune related toxicities as well as an increased risk of mucosal bleeding as documented in the informed consent and protocol and shared with the FDA, only those SAEs that are unexpected will be reported to the Sponsor in an expedited manner.

The PI will submit a summary table of all grade 3-5 events, whether or not considered related to the product, every 6 months. The report shall include the number of participants treated in the timeframe, the number of events per AE term per grade which occurred in the 6-month timeframe and in total since the start of the study, attribution, and type/category of serious.

Reports will be submitted to the Center for Cancer Research (CCR) at [contact].

The Sponsor might request case summaries for those events if, upon review, the Sponsor determines that an aggregate safety report is required (21CFR312.32(c)(1)(iv)).

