10.4.5 Safety Analyses

Safety endpoints will be analyzed as summary statistics during treatment and/or as change scores from baseline assessments. AEs will be coded as defined in the Medical Dictionary for Regulatory Activities (MedDRA). All AEs will be recorded and tabulated following each treatment. AEs will be recorded by severity, frequency, and relationship to the study intervention and will be presented by System Organ Class (SOC) designations and preferred term groupings. Information on each AE will include start date, stop date, severity, relationship, expectedness, outcome, and duration. Adverse events leading to premature discontinuation from the study intervention and serious treatment-emergent AEs will be presented either in a Table or a Listing.

In addition, overall safety will be assessed by descriptive analyses using tabulated frequencies of AEs by grade using CTCAE Version 5 within dose cohorts and for the overall study population in terms of treatment-emergent AEs, SAEs, and clinically significant changes in safety laboratory tests, physical examinations, ECGs, and vital signs.

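### Section 6.1 has no CTCAE-grade criterion for recording laboratory abnormalities as AEs, so the Grade 3 limb of the Phase 2 halting rule and the graded safety tables can miss asymptomatic high-grade values

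*Combined protocol and SAP*

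**What the plan says.** **Recording (6.1).** "An abnormal laboratory value will be recorded in the database as an AE only if the laboratory abnormality is characterized" by one of these: discontinuation from the study, clinical signs or symptoms, a need for treatment, association with death or another SAE, or investigator judgement ("Is judged by the Investigator to be of significant clinical impact"). A last item asks for details when a result is considered clinically significant. No item refers to CTCAE grade.

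**Definition (8.1.1).** The general AE definition includes an abnormal laboratory finding and attaches none of these conditions.

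**Halting (3.3.3, Phase 2).** Accrual halts on vaccine-related reactions in two participants. The Grade 4 limb reads "Grade 4 (except for laboratory values that are asymptomatic or resolve to Grade" 1 or baseline within 7 days). The Grade 3 limb reads "or of Grade 3 not resolving to Grade ≤ 1 or baseline within 7 days in two participants", with no laboratory exemption.

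**DLT (3.1.1).** Asymptomatic laboratory values are exempt at both Grade 3 and Grade 4.

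**Sponsor table (8.4).** "The PI will submit a summary table of all grade 3-5 events, whether or not considered related to the product, every 6 months". The counts are per AE term and per grade.

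**Analysis (10.4.2, 10.4.5).** Phase I toxicities are described by grade and type. More generally, "overall safety will be assessed by descriptive analyses using tabulated frequencies of AEs by grade using CTCAE Version 5". Section 10.4.5 also lists clinically significant laboratory changes, and allows summary statistics or change scores from baseline.

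**The concern.** Several safety outputs are defined by grade, but entry to the AE database is not. For an asymptomatic, untreated laboratory value, the only route in is one investigator's view of its importance. Two things are at stake.

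- **The halt.** The Grade 3 limb of 3.3.3 can name an event that 6.1 does not require anyone to record. If the AE record is used to check the rule, a second qualifying participant could go unnoticed.
- **The reported rates.** Toxicity by grade is the Phase I primary description, and safety is a Phase II secondary objective. A table said to hold every Grade 3-5 event, and AE tables by grade, would depend partly on discretion. A zero in such a table could mean that no event occurred or that none was recorded.

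**Working it through.** The plan gives no figure for this point, so the main check is to follow one type of event through the rules. Take an asymptomatic, untreated laboratory value.

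**1. Can it stay out of the AE database?** Yes, at any grade, unless the investigator judges it important. The discontinuation item in 6.1 would not normally bring it in, because 3.3.1 exempts asymptomatic Grade 3 and Grade 4 laboratory values from mandatory treatment discontinuation.

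**2. Which rules would count it?**

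| Rule | Asymptomatic Grade 3 value, vaccine-related, over 7 days | Asymptomatic Grade 4 value |
|---|---|---|
| 3.1.1 DLT | Exempt | Exempt |
| 3.3.3 Phase 2 halt | Counts | Exempt |
| 8.4 table | In scope by its wording, but counted by AE term | Same |
| 10.4.5 AE by grade | Only if recorded as an AE | Only if recorded as an AE |

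The halt conflicts with 6.1 in one cell only: persistent vaccine-related Grade 3. The 8.4 table can fall short of its stated scope. The 10.4.5 tables are consistent with 6.1 but take over its gap, because the separate laboratory item is also limited to clinically significant changes and no shift table by grade is specified.

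**3. Scale, for illustration only.** Inputs: n = 22 Phase II participants (20 oropharyngeal + 2 sinonasal, from 10.2) and a threshold of two participants (3.3.3). Two inputs are assumptions with no source in the documents: p, the chance that a participant has a qualifying Grade 3 event, and c, the fraction of such events recorded.

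P(at least 2) = 1 − (1 − pc)^22 − 22·pc·(1 − pc)^21

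With p = 0.05 and c = 1: 1 − 0.3235 − 0.3746 = 0.302.

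| p | All recorded (c = 1) | Half recorded (c = 0.5) | None recorded (c = 0) |
|---|---|---|---|
| 3% | 0.140 | 0.043 | 0 |
| 5% | 0.302 | 0.104 | 0 |
| 10% | 0.661 | 0.302 | 0 |

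With n = 20 the c = 1 values at 5% and 10% are 0.264 and 0.608.

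**4. What the trial's own data say about p.** Table 8 (14.1.2) reports no PRGN-2009-related event of Grade 3 or higher in 22 Phase 2 participants. Taken at face value, the one-sided 95% upper bound is 1 − 0.05^(1/22) = 12.7%, so the assumed 3-10% is not ruled out. Nor is it supported. If those counts were collected under the 6.1 rule, they cannot separate absence from non-recording for this kind of event.

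**The case against.** The strongest reply is that 6.1 permits the omission but does not cause it. The halt is triggered by a treatment-related reaction, so an investigator must already have seen the value and attributed it to the vaccine. Section 7.5.1 has the team discuss each participant about weekly, and the Phase II calendar schedules biochemistry at treatment and safety visits. No section says that the halt is read only from the AE database. For the rule to fail, the same investigator would have to attribute a persistent Grade 3 value to the vaccine, yet neither judge it important nor raise it. All of this stands. It makes a missed halt less likely but does not rule it out.

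The data also give some reassurance. Table 9 lists six laboratory-type events in Phase 2 (anemia 2, lymphocyte count decreased 2, creatinine increased 1, hyponatremia 1). Table 8 shows two Phase 2 events at Grade 3 and none higher, so at least 6 − 2 = 4 of the six were Grade 1-2. Low-grade laboratory values do reach the AE data. Table 8 also already covers 22 Phase 2 participants, which equals the planned 20 + 2. The halting question is therefore largely retrospective, apart from any replacement participants.

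On 8.4, the word 'all' may be meant to address attribution only, since the counts are by AE term. That reading is possible, but the scope should then be stated. On 8.1.1, a general definition can coexist with a narrower recording rule, so that difference alone is not an error.

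**Conclusion.** The point holds in a limited form. Section 6.1 leaves the recording of asymptomatic, untreated Grade 3-4 laboratory values to judgement. One limb of the Phase 2 halt can count a value that need not be recorded, and the 8.4 and graded AE tables can be incomplete. The percentages shown rest entirely on assumed event rates and recording fractions. The documents do not allow the size of any undercount to be derived.

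A reader might infer more, and the documents do not support it:

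- *That laboratory toxicity is in fact undercounted.* Nothing shows this. Judgement can bring a value in, and summary statistics or change scores may report laboratory data outside the AE terms.
- *That the halt counts asymptomatic laboratory values of any grade.* Section 3.3.3 exempts them at Grade 4.
- *That DLT or RP2D decisions are at risk.* Section 3.1.1 exempts asymptomatic values at both grades, so only the descriptive Phase I toxicity table is touched.
- *That 10.4.5 counts values that 6.1 leaves out.* It tabulates recorded AEs and clinically significant laboratory changes, in line with 6.1.

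The change is still worth making, because it makes the graded safety tables less dependent on discretion at very little cost.

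**What to change.** 1. Add one item to the 6.1 list: the value is CTCAE Grade 3 or higher and worse than the baseline grade, whether or not there are symptoms or treatment. Alternatively, tabulate laboratory shifts by CTCAE grade from the laboratory data already collected.
2. State that this set feeds the 8.4 six-monthly table and the graded tables under 10.4.5.
3. Do not define the 3.3.3 halt by this set. It would include the asymptomatic Grade 4 values that 3.3.3 exempts. Leave the exemptions in 3.3.3 and 3.1.1 untouched by the data rule, and apply each section's own conditions to the recorded events.
4. Separately, ask the sponsor to reconcile 3.3.3, which does not exempt asymptomatic Grade 3 laboratory values, with 3.1.1, which does. Which treatment is right is a clinical decision and is not proposed here.

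The cost is one line in 6.1 and a few more AE entries or one extra table, using bloods already drawn, so it can also be applied to participants already treated. The downside is that reported Grade 3-4 rates may look slightly higher.
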